Appendix C: Details of GLI Equations for Calculating ppFEV₁

Percent predicted values will be calculated for parameters of FEV₁, FVC, FEV₁/FVC, and FEF_{25%-75%} using the Quanjer GLI-2012 Regression Equations and Lookup Tables.

The regression equations and lookup tables required to implement the Quanjer GLI-2012 predicted values are available in:

Philip H. Quanjer, Sanja Stanojevic, Tim J. Cole, Janet Stocks. Quanjer GLI-2012 Regression Equation and Lookup Tables (Version 7 April 2013). Global Lung Function Initiative. [online] Available at: <http://www.ers-education.org/home/browse-all-content.aspx?idParent=138978> [Accessed Jul. 9, 2019].

The instructions and tools on how to implement the Quanjer GLI-2012 equations are:

Philip H. Quanjer, Sanja Stanojevic, Tim J. Cole, Janet Stocks. Implementing GLI-2012 regression equations (Version 19 July 2015). Global Lung Function Initiative. [online] Available at: <http://www.ers-education.org/home/browse-all-content.aspx?idParent=138979> [Accessed Jul. 9, 2019].

Sanja Stanojevic. GLI-2012 - SAS Macro (Version 2, 7 April 2013). Global Lung Function Initiative. [online] Available at: <http://www.ers-education.org/home/browse-all-content.aspx?idParent=138988> [Accessed Jul. 9, 2019].

Data handling rule for spirometry is as follows:

- Input age with at least 2 decimal place
- Use height at screening regardless if height is collected at other study visits for subjects whose age at informed consent is >21 years. For subjects with age <=21 years, height collected at the respective visit should be used.
- For race, map CRF black or AA to black, all other races in CRF (except white) are mapped to 'other'; multiple checks for race in CRF are also mapped to 'other'; white is a reference race in the equations and assumes 0 values for all race coefficients in the GLI equations.

Appendix D: Steps for Multiple Imputation

For the multiple imputation (MI) to be applied to the MMRM model for the primary efficacy endpoint, the following steps will be followed:

Imputation distribution

The imputation distribution for the missing absolute change from baseline in ppFEV₁ at visit t will be a normal distribution. All randomized subjects will be classified into one of three categories based on the following rules:

- Non-missing category: Subjects who have a ppFEV₁ assessment at Week 8 (i.e., subjects who have a non-missing absolute change from baseline in ppFEV₁ at Week 8).
- Missing category 1: Subjects with missing absolute change from baseline in ppFEV₁ at Week 8, who discontinued treatment because of adverse events, noncompliance with study drug, death, or physician decision, or because the subject refused further dosing or required prohibited medication.
- Missing category 2: Subjects who discontinued treatment for any reason not listed in Category 1 and have missing absolute change from baseline in ppFEV₁ at Week 8, or subjects who have completed 8 weeks treatment duration but are missing the absolute change from baseline in ppFEV₁ at visit Week 8

Imputation algorithm

We will use the following algorithm that relates the mean of the missing absolute change from baseline in ppFEV₁ at visit t to the missing categories defined above. The algorithm will be implemented within each treatment group as follows:

- Missing category 1: randomly draw a sample from the normal distribution(μ_{25}, σ^2), where μ_{25} is the 25th percentile of the non-missing absolute changes from baseline in ppFEV₁ at visit t and σ^2 is the sample variance estimated using the non-missing absolute changes at visit t .
- Missing category 2: randomly draw a sample from the normal distribution(μ, σ^2), where μ is the mean of the non-missing absolute changes from baseline in ppFEV₁ at visit t and σ^2 is the sample variance estimated using the non-missing absolute changes at visit t .

Analysis model

The complete MI method is described below:

- Form an “imputed dataset” by imputing missing values at each visit for those subjects who have a missing value at the visit and have all subsequent values missing. The appropriate normal distribution specified in the algorithm above will be used for each such subject, based on their category.
- Repeat this process K ($K=20$) times to form K imputed datasets.
- Fit the same MMRM model to each imputed dataset to estimate the absolute change at Week 8.
- Combine the results from the K imputed datasets using the SAS procedure MIANALYZE to derive the MI estimator.

Let θ be the true treatment difference. Denote by $\tilde{\theta}_k$ the estimate of θ from the k^{th} imputed dataset, and the corresponding estimate of the variance is denoted by \tilde{v}_k . The MI estimator of θ , $\tilde{\theta}_{\text{MI}}$, is the average of the K individual estimates.

The estimated variance of $\tilde{\theta}_{\text{MI}}$ is a combination of the between- and within-imputation variability as follows: $\tilde{v}_{\text{MI}} = \tilde{v} + \left(1 + \frac{1}{K}\right) \tilde{v}_w$, where $\tilde{v}_w = \frac{1}{K} \sum_{k=1}^K \tilde{v}_k$ is the within-imputation variability and is $\tilde{v} = \frac{1}{K-1} \sum_{k=1}^K (\tilde{\theta}_k - \tilde{\theta}_{\text{MI}})^2$ is the between-imputation variance. The statistic $T = \frac{\tilde{\theta}_{\text{MI}} - \theta}{\sqrt{\tilde{v}_{\text{MI}}}}$ has an approximate $t_{\tilde{v}}$ distribution, where $\tilde{v} = (K - 1) \left(1 + \frac{W}{B}\right)^2$.

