9.3.1.2 Primary Analysis

The primary analysis will be performed using a mixed-effects model for repeated measures (MMRM) with the absolute change from baseline at Day 15, Week 4 and Week 8 as the dependent variable. The model will include treatment group, visit, and treatment-by-visit interaction as fixed effects, with continuous baseline ppFEV₁, continuous baseline SwCl, and comparator group (IVA comparator versus TEZ/IVA comparator) as covariates. The Day 15 Visit will not be included in the estimation of the average treatment effect through Week 8. The model will be estimated using restricted maximum likelihood. Denominator degrees of freedom for the *F*-test for fixed effects will be estimated using the Kenward-Roger approximation². An unstructured covariance structure will be used to model the within-subject errors. If the model estimation does not converge, a compound symmetry covariance structure will be used instead. Conditional on the observed data and covariates, missing data will be assumed to be missing at random; consequently, no imputation of missing data will be performed.

The primary results obtained from the model will be the estimated within-group treatment difference through Week 8 (average of Week 4 and Week 8) for the ELX/TEZ/IVA group. The adjusted means with 2-sided 95% confidence intervals and 2-sided *P* values will be provided. Furthermore, the within-group treatment difference at each post-baseline visit will also be provided, obtained from the model.

The adjusted mean (with SE) obtained from the MMRM analysis at each post-baseline visit up to Week 8 will be plotted by treatment group.

The primary analysis will be conducted with the clinic spirometry data only. An additional analysis may also be performed to include pooled spirometry data obtained in clinic and by Air Next Spirometer, if the Air Next Spirometry data are assessed to be reasonably consistent with clinic spirometry data.

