9.3.1.3 Supportive Analysis

There will be no supportive analysis for the primary efficacy endpoint.

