9.3.1.4 Sensitivity Analysis

MMRM based on Multiple Imputation (MI)

An underlying assumption of the MMRM method is that data are missing at random. To minimize the amount of missing data, subjects who prematurely discontinue study drug treatment will continue to complete all scheduled study visits for spirometry and other efficacy assessments.

To assess the impact of missing data and the assumption that data are missing at random, a multiple imputation algorithm will be used if at least 10% of the subjects have missing changes in ppFEV₁ at Week 8 in any treatment group. Missing absolute change from baseline in ppFEV₁ assessments will be imputed starting from the first visit with missing values, for which all subsequent visits through Week 8 are also missing. For intermediate missing data, i.e., missing values that fall between two non-missing ones, it is reasonable to assume that they are missing at random and therefore will not be imputed. An MMRM analogous to that for the primary analysis of the primary endpoint will be applied to each imputed dataset and the relevant MI estimators will be reported. Details for the MI steps are presented in [Appendix D](#).

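### The one planned missing-data check of the primary endpoint names Week 8 instead of the Week 4/Week 8 average, and because it ignores each subject's own data it can, but need not, be more favourable than the MAR analysis it tests

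*SAP*

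**What the plan says.** SAP 9.3.1.2 gives the primary result as the "estimated within-group treatment difference through Week 8 (average of Week 4 and Week 8") in the ELX/TEZ/IVA arm, from an MMRM that assumes data are missing at random. The same section adds that "the within-group treatment difference at each post-baseline visit will also be provided, obtained from the model". SAP 9.3.1.3 states: "There will be no supportive analysis for the primary efficacy endpoint".

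SAP 9.3.1.4 then sets out one sensitivity analysis. Its purpose is "To assess the impact of missing data and the assumption that data are missing at random". It runs "if at least 10% of the subjects have missing changes in" ppFEV₁ at Week 8 in either arm. Only values missing from some visit onward through Week 8 are imputed; gaps between observed visits are left alone. The analysis is described this way: "An MMRM analogous to that for the primary analysis of the primary endpoint will be applied to each imputed dataset". The estimate to be reported is not named.

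Appendix D gives the steps. For each visit and arm, Category 1 subjects (stopped for adverse events, noncompliance, death, physician decision, refusal or prohibited medication) receive normal draws centred on the arm's observed 25th percentile. Category 2 subjects (other reasons, or completers without a Week 8 value) receive draws centred on the arm's observed mean. Both use the arm's observed variance. The last steps are "Fit the same MMRM model to each imputed dataset to estimate the absolute change at Week 8" and to combine 20 imputations, with theta described as a treatment difference.

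**The concern.** There are two separate defects.

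**Target.** Appendix D names a single visit and a difference. The primary result is a two-visit average within one arm. A programmer who follows Appendix D literally produces no sensitivity result for the primary estimate.

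**Draws.** The primary MMRM uses each subject's earlier visits, baseline ppFEV₁, baseline SwCl and comparator group. The Appendix D draws use none of these, and they treat the estimated mean, percentile and variance as known. Category 2 is therefore valid only if missingness is unrelated to earlier response within the arm, which is a stronger assumption than MAR. The Category 1 penalty is measured from the arm, not from what the subject was likely to show, so a subject already far below the arm can be drawn upward.

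A check intended to stress MAR should not come out more favourable than the MAR analysis. If it does, a reassuring result would be read as robustness that it does not show.

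**Working it through.** **Inputs from the documents.** 125 subjects in the arm, SD 7.0, change 3.0, 10% dropout, 2-sided 0.05 (protocol 12.1, SAP 7.2); 10% trigger (SAP 9.3.1.4); draw rules and K = 20 (Appendix D).

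**Assumptions not in the documents.** SD 7 at each visit, equal visit correlation r of 0.5 or 0.7, true change 3.0 at every visit, 11% missing at Weeks 4 and 8. Dropout after Day 15 follows a probit model with slope s = 0, 0.3, 0.6 or 1.0 per SD of poorer Day 15 change. One arm, no baseline covariates.

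**1. The plan's own figure.** 125 × 0.9 = 112.5. At n = 112 the noncentrality is (3.0/7.0) × √112 = 4.54 and power is 99.44% (99.47% at 113). The stated figure of more than 99% reproduces.

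**2. Trigger.** 12/125 = 9.6% and 13/125 = 10.4%, so 13 subjects are needed. At a 10% missing rate, the binomial chance of 13 or more is 48.4% per arm, and 1 - (1 - 0.484)² = 73% for at least one of two arms. At 8% it is 36%, at 5% it is 2%.

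**3. One subject.** The MAR prediction for a subject whose Day 15 change lies g points below the arm mean is r × g below the arm mean. The Category 1 centre is 0.674 × 7 = 4.7 below. The Category 1 draw is centred above the MAR prediction once g exceeds 4.72/r, which is 9.4 points (r = 0.5) or 6.7 points (r = 0.7).

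**4. The arm.** Dropouts' Day 15 mean lies d SDs below the arm, with d = s/√(1 + s²) × φ(c)/0.11, c = Φ⁻¹(0.11) and φ(c)/0.11 = 1.709. This gives d = 0, 0.491, 0.879 and 1.209, that is, mean Day 15 changes among dropouts of about 3.0, -0.4, -3.2 and -5.5. Slope 1.0 is an extreme case.

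Category 2 draws reproduce the completers' mean, so Appendix D minus MAR = r × 7 × (0.11/0.89) × d. At s = 0.3 this is 0.21 (r = 0.5) and 0.30 (r = 0.7). A Category 1 share f subtracts f × 0.11 × 4.72 = f × 0.52.

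**5. A linked case.** Suppose 5.5% stop for response-related reasons (all Category 1) and 5.5% are unrelated gaps (all Category 2). The difference is r × 7 × (0.055/0.945) × d′ - 0.055 × 4.72, where d′ uses φ(c′)/0.055 = 2.023, with c′ = Φ⁻¹(0.055), so d′ = 0, 0.581, 1.041 and 1.430. At s = 1.0 and r = 0.7: 4.9 × 0.0582 × 1.430 - 0.26 = +0.15.

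**6. Simulation, 2000 arms per setting.** Appendix D minus MAR for the Week 4/Week 8 average, in points (r = 0.5 / r = 0.7):

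| Category mix | s = 0 | s = 0.3 | s = 0.6 | s = 1.0 |
|---|---|---|---|---|
| All Category 2 | 0.00/0.01 | +0.22/+0.29 | +0.39/+0.53 | +0.52/+0.73 |
| Half Category 1, at random | -0.26/-0.26 | -0.04/+0.04 | +0.13/+0.29 | +0.28/+0.48 |
| All Category 1 | -0.52/-0.52 | -0.30/-0.21 | -0.13/+0.03 | +0.02/+0.23 |
| Linked case | -0.25/-0.26 | -0.14/-0.09 | -0.04/+0.04 | +0.04/+0.16 |

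The formulas in steps 4 and 5 agree with every cell to within about 0.02. At s = 0.6, Appendix D is more favourable than MAR in 83%/96% of arms when half are Category 1 at random, but in only 34%/61% in the linked case. In the first three rows, the bias at Week 8 alone is about the same size as for the average.

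**7. Effect on the test.** With the first three mixes, and with either both visits or only Week 8 missing (48 scenarios), Appendix D still rejects the null in at least 97.5% of arms for the average and 94.7% for Week 8.

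**The case against.** The target mismatch can be called a wording slip. SAP 9.3.1.4 asks for an MMRM analogous to the primary one, the average is a contrast from the same fit, and the primary analysis reports each visit, so a like-for-like Week 8 comparison will exist. This stands as mitigation. It does not remove the conflict between Appendix D and the primary definition.

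A reader might infer that the check always flatters the result when dropout depends on response. The documents do not support that. Appendix D sends most response-related stopping reasons to Category 1, where the difference is negative or near zero except at steep slopes, and Category 2 includes completers with a missed visit. In the linked case the mean excess is at most about 0.16 points, and only at the extreme slope. Gaps unrelated to response give essentially no Category 2 bias.

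Further limits also stand. Follow-up continues after stopping: "subjects who prematurely discontinue study drug treatment will continue to complete all scheduled study visits for spirometry and other efficacy assessments". The optional pooled analysis with home spirometry could fill some missed clinic visits, although it concerns data source and does not test MAR. The documents give no visit correlation or dropout slope, so what counts as moderate dropout is a matter of judgement.

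**Conclusion.** Both defects hold on the text. Followed literally, Appendix D estimates a different quantity from the primary result. Its draws also omit the subject-level information that the MAR analysis uses. The direction is conditional: the check can be more favourable than MAR when poor early responders are lost, and is conservative under Category 1 when dropout is unrelated to early response. The size rests on the assumed SD, correlation, missing fraction and slope. The plausible range is a few tenths of a point either way, against an assumed effect of 3.0.

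A reader might also infer that the primary conclusion is at risk. It is not, on these figures. Under subject-level imputation with dropout after Day 15, the common downward shift that brings the lower 95% limit to 0 has a median of about 14 points (5th to 95th percentile about 5 to 27). The loss is in the check's evidential value. The point is minor, but worth correcting because no other planned analysis tests the MAR assumption for this endpoint.

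**What to change.** Amend Appendix D before unblinding:

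- **(a) Target.** Set the estimate and theta to the within-group Week 4/Week 8 average for ELX/TEZ/IVA. Week 8 may be kept as an extra.
- **(b) Imputation.** Within arm, impute by sequential regression on earlier visits, baseline ppFEV₁, baseline SwCl and comparator group, with the regression parameters drawn for each imputation.
- **(c) Category 1.** Apply the penalty as a downward shift from the subject's conditional draw, subtracted after drawing so that it is not carried into the next visit. Fix the rule in advance, for example arm mean minus 25th percentile at that visit. In simulation with dropout after Day 15, this keeps the penalty at -0.50 to -0.53 (all Category 1) or -0.24 to -0.27 (half) at every slope.
- **(d) Both categories.** Unshifted Category 2 imputation only repeats MAR, so add a short prespecified grid of shifts applied to both categories. If a tipping point is wanted, prespecify only the search rule, because its value depends on unblinded data.

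Cost: SAP wording, a standard multiple-imputation program and one table. No extra data or subjects.

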Appendix E: Imputation Rules for Missing AE dates

Imputation rules for missing or partial AE start date are defined below. If the imputed AE start date is before the informed consent date, the AE start date will be imputed using the study informed consent date.

- **If only Day of AE start date is missing:**

- If the full (or partial) AE end date is NOT before the first dose date of the Treatment Period or AE end date is missing, then
 - if AE start year and month are equal to the month and year of first dose date of the Treatment Period, then impute the AE start day as the day of first dose date of the Treatment Period;
 - else if AE start year and month are equal to the month and year of first dose date of the Run-in Period, then impute the AE start day as the day of first dose date of the Run-in Period;
 - else impute the AE start day as 1.
- else if the full (or partial) AE end date is NOT before the first dose date of the Run-in Period, then
 - if AE start year and month are equal to the month and year of first dose date of the Run-in Period, then impute the AE start day as the day of first dose date of the Run-in Period;
 - else impute the AE start day as 1.
- else impute the AE start day as 1.

Compare the imputed AE start date with TE period to determine whether the AE is pretreatment AE, TEAE during the Run-in Period, TEAE during the Treatment Period, or post-treatment AE.

- **If Day and Month of AE start date are missing:**

- If the full (or partial) AE end date is NOT before the first dose date of the Treatment Period or AE end date is missing, then
 - if AE start year is equal to the year of first dose date of the Treatment Period, then impute the AE start month and day as the month and day of first dose date of the Treatment Period;
 - else if AE start year is equal to the year of first dose date of the Run-in Period, then impute the AE start month and day as the month and day of first dose date of the Run-in Period;
 - else impute the AE start month as January and day as 1.
- else if the full (or partial) AE end date is NOT before the first dose date of the Run-in Period, then
 - if AE start year is equal to the year of first dose date of the Run-in Period, then impute the AE start month and day as the month and day of first dose date of the Run-in Period;

- else impute the AE start month as January and day as 1.
- else impute the AE start month as January and day as 1.

Compare the imputed AE start date with TE period to determine whether the AE is pretreatment AE, TEAE during the Run-in Period, TEAE during the Treatment Period, or post-treatment AE.

- **If Year of AE start date is missing:**

If the year of AE start is missing or AE start date is completely missing then query site and

- If the full (or partial) AE end date is NOT before the first dose date of the Treatment Period or AE end date is missing, then impute the AE start date as the date of first dose date of the Treatment Period.
- else if the full (or partial) AE end date is NOT before the first dose date of the Run-in Period, then impute the AE start date as the date of first dose date of the Run-in Period.
- else impute AE date as the informed consent date.

The imputation should ensure the imputed AE start date is not before the informed consent date.

Imputation rules for partial AE end date are defined below:

If partial end date, then impute as min (the last day of the month, end of study participation) if day is missing, or min (Dec, end of study participation) if month is missing.

Appendix F: Criteria for Threshold Analysis

Table 12-3 Threshold Analysis Criteria for Laboratory Tests (as applicable)

Parameter	Threshold Analysis	Comments
Clinical Chemistry (LFT)		
ALT	>ULN - ≤3xULN >3x - ≤ 5xULN >5x - ≤ 8xULN >8x - ≤ 20.0xULN >20.0xULN	FDA DILI Guidance Jul 2009.
AST	>ULN - ≤3xULN >3x - ≤ 5xULN >5x - ≤ 8xULN >8x - ≤ 20.0xULN >20.0xULN	FDA DILI Guidance Jul 2009.
ALT or AST	(ALT>ULN - ≤3xULN) or (AST>ULN - ≤3xULN) (ALT>3x - ≤5xULN) or (AST>3x - ≤5xULN) (ALT>5x- ≤8xULN) or (AST>5x - ≤ 8xULN) (ALT>8x - ≤20xULN) or (AST>8x - ≤ 20xULN) ALT>20xULN or AST> 20xULN	FDA DILI Guidance
Alkaline Phosphatase	>ULN - ≤1.5xULN >1.5x - ≤2.5xULN >2.5x - ≤5.0 x ULN >5.0x - ≤20.0 x ULN >20.0xULN	FDA DILI Guidance Jul 2009.
Total Bilirubin	>ULN - ≤1.5xULN >1.5x - ≤2xULN >2x - ≤3xULN >3x - ≤10xULN >10xULN	FDA DILI Guidance Jul 2009.
Direct Bilirubin	>ULN - ≤ 1.5xULN >1.5x - ≤ 2xULN >2x - ≤ 3xULN >3x - ≤ 10xULN >10xULN	FDA DILI Guidance Jul 2009.
ALT and Total Bilirubin	ALT>3xULN and TBILI>2xULN	FDA DILI Guidance Jul 2009.
AST and Total Bilirubin	AST>3xULN and TBILI>2xULN	FDA DILI Guidance Jul 2009.
(ALT or AST) and Total Bilirubin	(ALT>3xULN or AST>3xULN) and TBILI>2xULN	FDA DILI Guidance Jul 2009.

Table 12-3 Threshold Analysis Criteria for Laboratory Tests (as applicable)

Parameter	Threshold Analysis	Comments
GGT	>ULN - ≤2.5xULN >2.5x - ≤5.0xULN >5.0x - ≤20.0xULN >20.0xULN	CTCAE grade 1-4
Clinical Chemistry (NON-LFT)		
Albumin	<LLN - ≥ 30 g/L <30 - ≥ 20 g/L <20 g/L	CTCAE grade 1-3
Amylase	>ULN - ≤1.5xULN >1.5x - ≤2xULN >2x - ≤5xULN >5xULN	Criteria based upon CTCAE
Creatinine	>ULN - ≤ 1.5xULN >1.5x - ≤ 3.0xULN >3.0x - ≤ 6.0xULN >6.0xULN	CTCAE grades 1-4
Lipase	>ULN - ≤1.5xULN >1.5x - ≤2xULN >2x - ≤5xULN >5xULN	Criteria based upon CTCAE
Total protein	<LLN >ULN	No CTCAE
Creatine kinase	>ULN - ≤2.5xULN >2.5x - ≤5xULN >5x - ≤10xULN >10xULN	CTCAE grades 1-4
Hematology		
Hemoglobin	Hgb decreased (anemia) <LLN - ≥ 100 g/L <100 - ≥ 80 g/L < 80 g/L	CTCAE grade 1-3
	Hgb increased >ULN - ≤ 20 g/L above ULN >20 g/L above ULN - ≤ 40 g/L above ULN >40 g/L above ULN	CTCAE grade 1-3
Platelets	Platelet decreased <LLN - ≥ 75.0 x 10e9 /L <75.0 - ≥ 50.0 x 10e9 /L <50.0 - ≥ 25.0 x 10e9 /L <25.0 x 10e9 /L	CTCAE grade 1-4
	Platelet increased >ULN	No CTCAE available

Table 12-3 Threshold Analysis Criteria for Laboratory Tests (as applicable)

Parameter	Threshold Analysis	Comments
Reticulocytes/Erythrocytes (%)	<LLN >ULN	No CTCAE
Coagulation		
Activated partial thromboplastin time (PTT)	>ULN - $\leq 1.5 \times$ ULN >1.5 - $\leq 2.5 \times$ ULN >2.5 x ULN	CTCAE grade 1-3
Prothrombin time (PT) International Normalized Ratio (INR)	>ULN - $\leq 1.5 \times$ ULN >1.5 - $\leq 2.5 \times$ ULN >2.5 x ULN	CTCAE grade 1-3

Table 12-4 Threshold Analysis Criteria for ECGs

Parameter	Threshold Analysis	Comments
HR	Bradycardia <50 bpm <45 bpm Decrease from baseline ≥ 10 bpm Decrease from baseline ≥ 20 bpm <50 bpm and decrease from baseline ≥ 10 bpm <50 bpm and decrease from baseline ≥ 20 bpm	Per HV grade 2, 3, plus shift change
	Tachycardia >100 bpm >115 bpm >130 bpm Increase from baseline ≥ 10 bpm Increase from baseline ≥ 20 bpm >100 bpm and increase from baseline ≥ 10 bpm >100 bpm and increase from baseline ≥ 20 bpm	Per HV grade 1, 2, 3, plus shift change
PR	≥ 240 ms ≥ 300 ms ≥ 200 ms and increase from baseline ≥ 40 ms ≥ 200 ms and increase from baseline ≥ 100 ms	
QRS	>110 ms >160 ms Increase from baseline ≥ 20 ms Increase from baseline ≥ 40 ms	

Table 12-4 Threshold Analysis Criteria for ECGs

Parameter	Threshold Analysis	Comments
QTc	>450 to <500ms (Male) or >470 to <500ms (Female) ≥500 ms Increase from baseline Increase from baseline >10 ms Increase from baseline >20 ms Increase from baseline >40 ms Increase from baseline >60 ms	To be applied to any kind of QT correction formula.

Table 12-5 Threshold Analysis Criteria for Vital Signs

Parameter	Threshold Analysis	Comments
Pulse Rate	Same as above in ECG category	
SBP increased	>140 mmHg >160 mmHg >10 mmHg increase from baseline >20 mmHg increase from baseline >140 mmHg & >10 mmHg increase from baseline >140 mmHg & >20 mmHg increase from baseline >160 mmHg & >10 mmHg increase from baseline >160 mmHg & >20 mmHg increase from baseline	809/770 analyses
SBP decrease	<90 mmHg <80 mmHg >10 mmHg decrease from baseline >20 mmHg decrease from baseline <90 mmHg and >10 mmHg decrease from baseline <90 mmHg and >20 mmHg decrease from baseline <80 mmHg and >10 mmHg decrease from baseline <80 mmHg and >20 mmHg decrease from baseline	Per HV grade 1, 3, plus shift change

Table 12-5 Threshold Analysis Criteria for Vital Signs

Parameter	Threshold Analysis	Comments
DBP increased	>90 mmHg	
	>100 mmHg	
	>5 mmHg increase from baseline	
	>10 mmHg increase from baseline	
	>90 mmHg and >5 mmHg increase from baseline	
	>90 mmHg and >10 mmHg increase from baseline	
	>100 mmHg and >5 mmHg increase from baseline	
DBP decreased	<60 mmHg	
	<45 mmHg	
	>5 mmHg decrease from baseline	
	>10 mmHg decrease from baseline	
	<60 mmHg and >5 mmHg decrease from baseline	
	<60 mmHg and >10 mmHg decrease from baseline	
	<45 mmHg and >5 mmHg decrease from baseline	
Weight	Weight gain	CTCAE grade 1-3
	≥5 % increase from baseline	
	≥10 % increase from baseline	
	≥20% increase from baseline	
Weight	Weight loss	CTCAE grade 1-3
	≥5 % decrease from baseline	
	≥10 % decrease from baseline	
	≥20% decrease from baseline	

Table 12-6 Threshold Analysis Criteria for Laboratory Tests (for labeling purpose)

Parameter	Threshold Analysis	Comments
Clinical Chemistry (LFT)		
ALT or AST	>3xULN	For labeling purpose
	>5xULN	
	>8xULN	

